Appendix 1 Glossary of Abbreviations

Glossary of Abbreviations:

ADA	American Diabetes Association
ADaM	Analysis Data Set
AE	Adverse Event
AIA	Anti-Insulin Antibodies
ALT	Alanine Aminotransferase
ANCOVA	Analysis of Covariance
AST	Aspartate Aminotransferase
ATC	Anatomical Therapeutic Classification
BID	Twice Daily
BMI	Body Mass Index
CDISC	Clinical Data Interchange Standard Consortium
CGM	Continuous Glucose Monitor
CI	Confidence Interval
CRF	Case Report Form
CTCAE	Common Terminology Criteria for Adverse Event
CTMS	Clinical Trial Management System
CV	Coefficient of Variation
ECG	Electrocardiogram
EIIPD	Efficacy-Interfering Important Protocol Deviation
EMA	European Medicines Agency
ERIPD	Eligibility-Related Important Protocol Deviation
EOT	End of Treatment
FAS	Full Analysis Set
FBG	Fasting Blood Glucose
FDA	Food and Drug Administration
HbA1c	Glycosylated Hemoglobin
Hgb	Hemoglobin
ICF	Informed Consent
IP	Investigational Product
ITT	Intention to Treat

Gan & Lee Pharmaceuticals USA

PRA HEALTHSCIENCES

Sponsor: Gan & Lee Pharmaceuticals, USA Corporation

Protocol no: GL-GLAT2-3002

Statistical Analysis Plan

Version Date: 16-Nov-2020

IIIPD	Immunogenicity-Interfering Important Protocol Deviation
IXRS	Interactive Web Response System
LLOQ	Lower Limit of Quantification
LGH	Laboratory-Grade Hyperglycemia
MAR	Missing at Random
MedDRA	Medical Dictionary for Regulatory Activities
MI	Multiple Imputation
MNAR	Missing Not at Random
MWG	Mean Weighted Glucose
NAb	Anti-insulin Neutralizing Antibody
NCI CTCAE	National Cancer Institute Common Terminology Criteria for Adverse Events
NGSP	National Glycohemoglobin Standardization Program
OAM	Other Antidiabetes Medication
OSADD	Overall Subject Average Daily Dose
PPS	Per Protocol Analysis Set
QD	Daily
QTc	Corrected QT interval
QTcB	Corrected QT interval using Bazett's formula
QTcF	Corrected QT interval using Fridericia's formula
RBC	Red Blood Cell
SAE	Serious Adverse Event
SAP	Statistical Analysis Plan
SD	Standard Deviation
SDTM	Study Data Tabulation Model
SDTMIG	Study Data Tabulation Model Implementation Guide
SI	International System of Units
SOC	System Organ Class
SS	Safety Analysis Set
T4	Free Thyroxine
TEAE	Treatment-Emergent Adverse Event
TFLs	Tables, Figures, and Listings
TOST	Two One-Sided Tests

Gan & Lee Pharmaceuticals USA

PRAHEALTHSCIENCES

Sponsor: Gan & Lee Pharmaceuticals, USA Corporation
Protocol no: GL-GLAT2-3002

Statistical Analysis Plan
Version Date: 16-Nov-2020

TSH	Thyroid-Stimulating Hormone
ULN	Upper Limit of Normal
WBC	White Blood Cell

Gan & Lee Pharmaceuticals USA

PRA HEALTH SCIENCES

Sponsor: Gan & Lee Pharmaceuticals, USA Corporation
Protocol no: GL-GLAT2-3002

Statistical Analysis Plan
Version Date: 16-Nov-2020

Appendix 2 NCI CTCAE v 4.03 Grading for Laboratory Values and QTc

SOC	AE Term	Grade 1	Grade 2	Grade 3	Grade 4
Investigations	White blood cell decreased (Leukopenia)	<LLN - 3000/mm ³ ; <LLN - 3.0 × 10 ⁹ /L	<3000 - 2000/mm ³ ; <3.0 - 2.0 × 10 ⁹ /L	<2000 - 1000/mm ³ ; <2.0 - 1.0 × 10 ⁹ /L	<1000/mm ³ ; <1.0 × 10 ⁹ /L
Investigations	White blood cell increased (Leukocytosis)	-	-	>100,000/mm ³	-
Blood and lymphatic system disorders	Anemia	Hemoglobin (Hgb) <LLN - 10.0 g/dL; <LLN - 6.2 mmol/L; <LLN - 100 g/L	Hgb <10.0 - 8.0 g/dL; <6.2 - 4.9 mmol/L; <100 - 80g/L	Hgb <8.0g/dL; <4.9 mmol/L; <80 g/L; transfusion indicated	Life-threatening consequences; urgent intervention indicated
Investigations	Lymphocyte count decreased (Lymphopenia)	<LLN - 800/mm ³ ; <LLN - 0.8 × 10 ⁹ /L	<800 - 500/mm ³ ; <0.8 - 0.5 × 10 ⁹ /L	<500 - 200/mm ³ ; <0.5 - 0.2 × 10 ⁹ /L	<200/mm ³ ; <0.2 × 10 ⁹ /L
Investigations	Neutrophil count decreased (Neutropenia)	<LLN - 1500/mm ³ ; <LLN - 1.5 × 10 ⁹ /L	<1500 - 1000/mm ³ ; <1.5 - 1.0 × 10 ⁹ /L	<1000 - 500/mm ³ ; <1.0 - 0.5 × 10 ⁹ /L	<500/mm ³ ; <0.5 × 10 ⁹ /L
Investigations	Platelet count decreased (Thrombocytopenia)	<LLN - 75,000/mm ³ ; <LLN - 75.0 × 10 ⁹ /L	<75,000 - 50,000/mm ³ ; <75.0 - 50.0 × 10 ⁹ /L	<50,000 - 25,000/mm ³ ; <50.0 - 25.0 × 10 ⁹ /L	<25,000/mm ³ ; <25.0 × 10 ⁹ /L
Investigations	Alkaline phosphatase increased	>ULN - 2.5 × ULN	>2.5 - 5.0 × ULN	>5.0 - 20.0 × ULN	>20.0 × ULN
Investigations	Alanine aminotransferase increased	>ULN - 3.0 × ULN	>3.0 - 5.0 × ULN	>5.0 - 20.0 × ULN	>20.0 × ULN
Investigations	Aspartate aminotransferase increased	>ULN - 3.0 × ULN	>3.0 - 5.0 × ULN	>5.0 - 20.0 × ULN	>20.0 × ULN

PRAHEALTHSCIENCES

Sponsor: Gan & Lee Pharmaceuticals, USA Corporation
 Protocol no: GL-GLAT2-3002

Statistical Analysis Plan
 Version Date: 16-Nov-2020

Investigations	Blood bilirubin increased	>ULN - 1.5 x ULN	>1.5 - 3.0 x ULN	>3.0 - 10.0 x ULN	>10.0 x ULN
Metabolism and nutrition disorders	Hypercalcemia	Corrected serum calcium of >ULN - 11.5 mg/dL; >ULN - 2.9 mmol/L; ionized calcium >ULN - 1.5 mmol/L	Corrected serum calcium of >ULN - 11.5 mg/dL; >ULN - 2.9 mmol/L; ionized calcium >ULN - 1.5 mmol/L	Corrected serum calcium of >12.5 - 13.5 mg/dL; >3.1 - 3.4 mmol/L; ionized calcium >1.6 - 1.8 mmol/L; hospitalization indicated	Corrected serum calcium of >13.5 mg/dL; >3.4 mmol/L; ionized calcium >1.8 mmol/L; life-threatening consequences
Metabolism and nutrition disorders	Hypocalcemia	Corrected serum calcium of <LLN - 8.0 mg/dL; <LLN - 2.0 mmol/L; ionized calcium <LLN - 1.0 mmol/L	Corrected serum calcium of <8.0 - 7.0 mg/dL; <2.0 - 1.75 mmol/L; ionized calcium <1.0 - 0.9 mmol/L; symptomatic	Corrected serum calcium of <7.0 - 6.0 mg/dL; <1.75 - 1.5 mmol/L; ionized calcium <0.9 - 0.8 mmol/L; hospitalization indicated	Corrected serum calcium of <6.0 mg/dL; <1.5 mmol/L; ionized calcium <0.8 mmol/L; life threatening consequences
Investigations	Creatinine increased	>1 - 1.5 x baseline; >ULN - 1.5 x ULN	>1.5 - 3.0 x baseline; >1.5 - 3.0 x ULN	>3.0 x baseline; >3.0 - 6.0 x ULN	>6.0 x ULN
Metabolism and nutrition disorders	Hyperglycemia	Fasting glucose value >ULN - 160 mg/dL; Fasting glucose value >ULN - 8.9 mmol/L	Fasting glucose value >160 - 250 mg/dL; Fasting glucose value >8.9 - 13.9 mmol/L	>250 - 500 mg/dL; >13.9 - 27.8 mmol/L; hospitalization indicated	>500 mg/dL; >27.8 mmol/L; life-threatening consequences
Metabolism and nutrition disorders	Hypoglycemia	<LLN - 55 mg/dL; <LLN - 3.0 mmol/L	<55 - 40 mg/dL; <3.0 - 2.2 mmol/L	<40 - 30 mg/dL; <2.2 - 1.7 mmol/L	<30 mg/dL; <1.7 mmol/L; life-threatening consequences; seizures
Metabolism and nutrition disorders	Hyperkalemia	Blood potassium value >ULN - 5.5 mmol/L	Blood potassium value >5.5 - 6.0 mmol/L	Blood potassium value >6.0 - 7.0 mmol/L; hospitalization indicated	Blood potassium value >7.0 mmol/L; life-threatening consequences
Metabolism and nutrition disorders	Hypokalemia	Blood potassium value <LLN - 3.0 mmol/L	Blood potassium value <LLN - 3.0 mmol/L; symptomatic; intervention indicated	Blood potassium value <3.0 - 2.5 mmol/L; hospitalization indicated	Blood potassium value <2.5 mmol/L; life-threatening consequences
Metabolism and nutrition disorders	Hyponatremia	Plasma sodium <LLN - 130 mmol/L	-	Plasma sodium <130 - 120 mmol/L	Plasma sodium <120 mmol/L; life-threatening consequences
Metabolism and nutrition disorders	Hypernatremia	Plasma sodium >ULN - 150 mmol/L	Plasma sodium >150 - 155 mmol/L	Plasma sodium >155 - 160 mmol/L; hospitalization indicated	Plasma sodium >160 mmol/L; life-threatening consequences

Gan & Lee Pharmaceuticals USA PRAHEALTHSCIENCES

Sponsor: Gan & Lee Pharmaceuticals, USA Corporation
Protocol no: GL-GLAT2-3002

Statistical Analysis Plan
Version Date: 16-Nov-2020

Metabolism and nutrition disorders	Hypertriglyceridemia	Serum triglycerids 150 mg/dL - 300 mg/dL; 1.71 mmol/L - 3.42 mmol/L	Serum triglycerids >300 mg/dL - 500 mg/dL; >3.42 mmol/L - 5.7 mmol/L	Serum triglycerids >500 mg/dL - 1000 mg/dL; >5.7 mmol/L - 11.4 mmol/L	Serum triglycerids > 1000 mg/dL; >11.4 mmol/L; life-threatening consequences
Investigations	Electrocardiogram QT corrected interval prolonged	QTc 450-480 ms	QTc 481-500 ms	QTc ≥ 501 ms on at least 2 separate ECGs	QTc ≥ 501 ms or >60 ms change from baseline and Torsade de pointes or polymorphic ventricular tachycardia or signs/symptoms of serious arrhythmia

AE = adverse event; CTCAE = Common Terminology Criteria for Adverse Events; ECG = electrocardiogram; Hgb = hemoglobin; LLN = lower limit of normal; QTc = corrected QT interval; SOC = system organ class; ULN = upper limit of normal;

Note: Laboratory measurements that are within the institutional limits of normal and are not graded as 1-4, per the CTCAE, will be summarized as "Grade 0" which is defined as normal.

Sponsor: Gan & Lee Pharmaceuticals, USA Corporation
Protocol no: GL-GLAT2-3002

Statistical Analysis Plan
Version Date: 16-Nov-2020

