### **10.5 Clinical Laboratory Testing**

The following routine clinical laboratory tests will be performed as indicated in [Table 1](#) and [Section 9](#).

- Complete blood count (red blood cell [RBC] count, white blood cell [WBC] count, hemoglobin, hematocrit, platelet count, RBC indices, and a 5-part WBC differential [percentages of neutrophils, lymphocytes, monocytes, eosinophils, and basophils])
- Chemistry metabolic panel, including glucose, creatinine, blood urea nitrogen, sodium, potassium, chloride, bicarbonate, calcium, total protein, total and conjugated bilirubin, alanine aminotransferase, aspartate aminotransferase, alkaline phosphatase, and creatine kinase
- Serum lipid panel including total cholesterol, low-density lipoprotein, high-density lipoprotein, and triglycerides
- TSH and free T4

The following additional blood tests will be performed at specific visits as outlined in [Table 1](#) and [Section 9](#). More information about sample collection and handling will be included in the respective laboratory manuals.

- AIA (blood should be collected before the subject administers insulin)
- FBG test (venous)
- HbA1c

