11.8.3.1 NCI CTCAE Grading

Where laboratory values are categorized into NCI CTCAE v4.03 grades, the categories are defined according to the criteria available on the following website:

<http://evs.nci.nih.gov/ftp1/CTCAE/About.html>

Note that grades are applied based only on the numeric SI value of the parameter assessed; clinical signs and symptoms are not considered. For example, Grade 4 hyperglycemia will be assigned based solely on the value of the glucose measurement, and acidosis will not be considered. Where categories are distinguished only by clinical signs or symptoms, the lowest of the possible grades will be assigned.

NCI CTCAE grades will be applied for the following lab parameters (as defined by the table in Appendix 2):

Hematology: hemoglobin (anemia), total WBC (leukopenia and leukocytosis), lymphocytes (lymphopenia), neutrophils (neutropenia), and platelets (thrombocytopenia).

Percent lymphocytes and percent neutrophils were specified in the original protocol and consequently absolute lymphocyte and neutrophil counts with corresponding normal ranges needed for the derivation of NCI CTCAE grading were not included in the central laboratory data transfers. Absolute counts for lymphocytes and neutrophils will be derived based on percent values and total WBC count as defined below only for the purpose of NCI CTCAE grading (Blumenreich, M. 1990 (9)). Calculated values will be rounded to the thousandths. NCI CTCAE grading will be derived in three steps: 1) grades 2-4 will be derived according to NCI CTCAE cutoffs, 2) if the reference range indicator for percent value indicates "LOW" and the derived absolute count is greater than 0.8 ($10^9/L$) for lymphocytes or 1.5 ($10^9/L$) for neutrophils then grade=1, and then 3) if the reference range indicator for percent value is 'NORMAL' then grade=0.

$$\text{Absolute lymphocyte count } (10^9/L) = (\text{total WBC } (10^9/L) * \% \text{ Lymphocyte})/100$$

$$\text{Absolute neutrophil count } (10^9/L) = (\text{total WBC } (10^9/L) * \% \text{ Neutrophil})/100$$

Chemistry: alkaline phosphatase, ALT, AST, bilirubin, calcium (hypocalcemia, hypercalcemia), creatinine, glucose (hyperglycemia, hypoglycemia), potassium (hyperkalemia, hypokalemia), sodium (hyponatremia, hypernatremia), and triglycerides (hypertriglyceridemia).

Laboratory measurements that are within the limits of normal and are not graded as 1-4, per the NCI CTCAE, will be coded as "Grade 0," which is defined as normal.

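### SAP Appendix 2 gives hypercalcemia Grades 1 and 2 the same limits, so calcium above 2.9 and up to 3.1 mmol/L has no grade

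*SAP*

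**What the plan says.** The hypercalcemia row of SAP Appendix 2 reads as follows.

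- Grades 1 and 2, in identical words: "Corrected serum calcium of >ULN - 11.5 mg/dL; >ULN - 2.9 mmol/L", with ionized calcium running from above the ULN to 1.5 mmol/L in both cells
- Grade 3: "Corrected serum calcium of >12.5 - 13.5 mg/dL; >3.1 - 3.4 mmol/L; ionized calcium >1.6 - 1.8 mmol/L", followed by a hospitalization qualifier
- Grade 4: "Corrected serum calcium of >13.5 mg/dL; >3.4 mmol/L; ionized calcium >1.8 mmol/L; life-threatening consequences"

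SAP Section 11.8.3.1 puts the table to use: "NCI CTCAE grades will be applied for the following lab parameters (as defined by the table in Appendix 2". Calcium is on the list that follows, in both directions. Four other provisions matter:

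- Grading uses the numeric SI value alone and disregards signs and symptoms (11.8.3.1).
- Grade 0 is for results inside the normal limits that carry no grade from 1 to 4 (11.8.3.1 and the note under the Appendix 2 table).
- The highest non-missing grade after randomization is tabulated by treatment group in the Safety Analysis Set for 15 parameters, calcium among them (11.8.3.1).
- Section 11.8.3.1 opens by pointing to the NCI CTCAE v4.03 web page as the definition of the categories. It therefore names two sources for the grades.

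**The concern.** Grades on a laboratory scale should cover every abnormal value once. Here the second cell repeats the first, and the third starts higher than the first one ends. That leaves an overlap at the bottom of the scale and a hole in the middle.

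What is at stake is the maximum-grade table for calcium. A result in the hole has no grade. If the program sets that result to missing, it drops out of a maximum taken over non-missing grades. SAP Section 11.8.3 schedules chemistry after randomization at Weeks 12 and 26. A subject with 3.0 mmol/L at Week 12 and a normal value at Week 26 would then appear with a maximum of Grade 0, which the SAP defines as normal.

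**Working it through.** The plan states no derived figure here to reproduce. The check is whether the printed intervals cover every value above the ULN exactly once.

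**Inputs** (SAP Appendix 2; lower limits exclusive, upper limits inclusive)

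| Grade | mmol/L | mg/dL | Ionized, mmol/L |
|---|---|---|---|
| 1 | >ULN to 2.9 | >ULN to 11.5 | >ULN to 1.5 |
| 2 | >ULN to 2.9 | >ULN to 11.5 | >ULN to 1.5 |
| 3 | >3.1 to 3.4 | >12.5 to 13.5 | >1.6 to 1.8 |
| 4 | >3.4 | >13.5 | >1.8 |

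The documents do not give the central laboratory's ULN for calcium. I assumed 2.50 to 2.65 mmol/L (10.0 to 10.5 mg/dL), and 1.30 to 1.35 mmol/L for ionized calcium.

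**Step 1: run values through the table as printed.**

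| Calcium, mmol/L | Grades matched |
|---|---|
| 2.70, 2.85, 2.90 | 1 and 2 |
| 2.91, 3.00, 3.10 | none |
| 3.11, 3.40 | 3 |
| 3.41 | 4 |

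The other scales behave the same way. In mg/dL, 11.5 matches Grades 1 and 2; 11.6, 12.0 and 12.5 match none; 12.6 matches Grade 3. For ionized calcium, 1.50 matches Grades 1 and 2; 1.55 and 1.60 match none; 1.61 matches Grade 3. Every assumed ULN gave the same pattern.

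**Step 2: size of the gap.** Width = lower limit of Grade 3 minus upper limit of Grades 1 and 2.

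- SI units: 3.1 − 2.9 = 0.2 mmol/L
- Conventional units: 12.5 − 11.5 = 1.0 mg/dL
- Ionized: 1.6 − 1.5 = 0.1 mmol/L

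The lower edge is exclusive: exactly 2.9 mmol/L (11.5 mg/dL) is still covered. Because grading uses the SI value, the operative gap is above 2.9 and up to 3.1 mmol/L.

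**Step 3: can Grade 0 absorb the gap?** No. Grade 0 requires a value within normal limits, and everything in the gap exceeds the ULN.

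**Step 4: is it a unit-conversion artefact?** At 4.008 mg/dL per mmol/L (a conversion factor not given in the documents), 11.5 / 4.008 = 2.869, 12.5 / 4.008 = 3.119 and 13.5 / 4.008 = 3.368. These round to the printed 2.9, 3.1 and 3.4, so the two scales agree and the hole is real in both.

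**Step 5: is this how the table is built elsewhere?** In seven other high-side rows (alkaline phosphatase, ALT, bilirubin, hyperglycemia, hyperkalemia, hypernatremia, triglycerides) the upper limit of each grade is the lower limit of the next. The mirror row, hypocalcemia, is also contiguous: below LLN to 2.0, then to 1.75, then to 1.5, then below 1.5 mmol/L. Among the rows checked, only hypercalcemia breaks.

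**The case against.** **The website as the standard.** Appendix 2 can be read as a transcription of the criteria that Section 11.8.3.1 cites, so a programmer working from the website need not follow the faulty cell. This stands in part. The effect on the output depends on which source is programmed. But the same section says the grades are applied as the appendix table defines them and gives no order of precedence, so the mismatch has to be resolved in the SAP.

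**Little is lost.** This largely stands. Calcium values and changes from baseline are still summarized, and shift tables against the reference range cover all laboratory assessments (SAP 11.8.3). Listings of Grade 3 or higher are intact because Grades 3 and 4 are intact. Results that the investigator judges clinically significant are recorded as adverse events (Protocol 11.5.1).

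**Stronger readings that a reader might infer.** One is that Grade 2 can never be assigned, because the SAP says "the lowest of the possible grades will be assigned". That rule is conditional: it covers categories that differ only in signs or symptoms. The hypercalcemia cells do not differ in anything, so the rule does not reach them, and values above the ULN up to 2.9 mmol/L are simply ambiguous. The row the rule does fit is hypokalemia, where Grade 2 repeats the Grade 1 limits but adds a symptom qualifier.

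Another is that corrected calcium could not be graded at all for want of albumin. Protocol 10.5 lists "Chemistry metabolic panel, including glucose, creatinine, blood urea nitrogen, sodium, potassium, chloride, bicarbonate, calcium, total protein" and further tests, but introduces them as inclusions, not as a complete panel. The SAP 11.8.3 list groups tests for summary and itself omits glucose and conjugated bilirubin, which the protocol names. Absence of albumin from these lists does not show that it was not measured.

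**Conclusion.** The point holds, as a minor but definite error in an operative table. As printed, calcium above 2.9 and up to 3.1 mmol/L (above 11.5 and up to 12.5 mg/dL; ionized above 1.5 and up to 1.6 mmol/L) has no grade and cannot be Grade 0. Calcium above the ULN and up to 2.9 mmol/L meets both Grade 1 and Grade 2.

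This rests on two assumptions: that the ULN is below 2.9 mmol/L, and that the duplicated cell is in the source PDF. A whole cell repeated across three scales is unlikely to be a text-extraction fault, but a glance at the PDF would settle it. The consequence for the output also assumes that the program follows Appendix 2.

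The documents give no expected number of subjects in the band, so the effect on counts cannot be estimated. It reaches only the maximum-grade summary for calcium. The primary immunogenicity analysis and the HbA1c analyses do not use these grades.

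**What to change.** In SAP Appendix 2, set hypercalcemia Grade 2 to the band that the table's own Grade 1 and Grade 3 limits leave open: >11.5 to 12.5 mg/dL; >2.9 to 3.1 mmol/L; ionized >1.5 to 1.6 mmol/L. The four grades are then contiguous and do not overlap.

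Check the corrected row against the CTCAE v4.03 source cited in Section 11.8.3.1, and add a sentence there saying which source governs if the two differ. Confirm that the grading program matches.

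The cost is one table cell, one sentence and a program check before database lock. No new data are needed and no other analysis changes.

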11.8.3 Laboratory Data

Laboratory test results will be reported in International System of Units (SI) units. For observed values below the lower limit of quantification/detection (for example total bilirubin reported as $<3 \mu\text{mol/L}$), the lower limit ($3 \mu\text{mol/L}$) will be used as the imputed value.

Laboratory values and change from baseline will be summarized using descriptive statistics by time point and treatment group. Hematology, chemistry, thyroid stimulating hormone (TSH) and free thyroxine (T4) results will be collected during screening, at visit Week 12 and visit Week 26.

Shift tables of the maximum post-baseline value will be presented by treatment group, reference range and time point. Shift tables will include all laboratory assessments. In addition, subject listings of abnormal (grade ≥ 3) post-baseline laboratory toxicities will be provided. Standard ranges from the central laboratory will be used for the laboratory analysis.

Lab assessments will be grouped for summary as follows:

- Hematology – white blood cell (WBC) parameters: WBC count and differentials
- Hematology – red blood cell (RBC) parameters: hemoglobin, hematocrit, RBC count, mean corpuscular hemoglobin, mean corpuscular hemoglobin concentration, mean corpuscular volume
- Hematology – other parameters: platelets
- Serum chemistry – hepatobiliary parameters: alanine aminotransferase (ALT), aspartate aminotransferase (AST), total bilirubin, alkaline phosphatase
- Serum chemistry – general chemistry: sodium, potassium, chloride, bicarbonate, total protein, calcium, creatine kinase, total cholesterol, high-density lipoprotein, low-density lipoprotein, triglycerides
- Serum chemistry – renal function tests: urea, creatinine
- Thyroid – free T4, TSH

A summary assessing the potential hepatotoxicity and potential Hy's Law will be presented. A listing of these potentially hepatotoxic values (along with the corresponding amount times upper limit normal) will be presented.

A treatment-related laboratory result listing including weight, HbA1c, fasting blood glucose, and immunogenicity results will be provided. Assessments after EOT visit will be flagged in the listing.

Positive pregnancy results and dip-stick urinalysis results will be provided in a listing.

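### SAP Appendix 2 grades calcium on corrected or ionized calcium, but neither document lists albumin or ionized calcium or says how uncorrected calcium is to be graded

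*SAP*

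**What the plan says.** SAP Appendix 2 sets the calcium grades. Grade 1 hypocalcemia is "Corrected serum calcium of <LLN - 8.0 mg/dL; <LLN - 2.0 mmol/L; ionized calcium <LLN - 1.0 mmol/L" and Grade 1 hypercalcemia is "Corrected serum calcium of >ULN - 11.5 mg/dL; >ULN - 2.9 mmol/L; ionized calcium >ULN - 1.5 mmol/L". The remaining calcium grades use the same two quantities, corrected serum calcium or ionized calcium. The appendix does not define the correction.

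SAP 11.8.3.1 makes that table operational. It names "calcium (hypocalcemia, hypercalcemia" among the chemistry parameters to be graded and states that "grades are applied based only on the numeric SI value of the parameter assessed". The maximum post-randomization grade for each of 15 parameters is then tabulated by arm in the Safety Analysis Set. SAP 11.8.3 also plans listings of post-baseline toxicities of Grade 3 or higher.

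For the inputs, Protocol 10.5 describes the panel as "Chemistry metabolic panel, including glucose, creatinine, blood urea nitrogen, sodium, potassium, chloride, bicarbonate, calcium, total protein, total and conjugated bilirubin", followed by liver enzymes and creatine kinase. SAP 11.8.3 groups the general chemistry analytes as "sodium, potassium, chloride, bicarbonate, total protein, calcium, creatine kinase, total cholesterol" and other lipids. Albumin and ionized calcium appear in neither place.

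**The concern.** The grading specification calls for a quantity that the listed data do not supply. A programmer who follows the SAP literally has calcium as reported, limits meant for corrected or ionized calcium, and no instruction for getting from one to the other. The easy course is to compare them directly and print the result as NCI CTCAE v4.03 hypo- or hypercalcemia. A reader of the maximum-grade table or the Grade 3 or higher listing could not tell that no correction had been made, and some grades could be wrong.

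The SAP treats the same kind of gap differently elsewhere. Section 11.8.3.1 notes that absolute lymphocyte and neutrophil counts were missing from the laboratory transfers, and supplies formulas, a three-step grading rule and a reference. Calcium has no comparable rule.

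**Working it through.** The plan states no figure to reproduce here, so the check is a comparison of sections followed by a labelled illustration.

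**1. Required inputs against listed inputs**

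| Item | Where | Content |
|---|---|---|
| Quantity graded | SAP Appendix 2 | Corrected serum calcium, or ionized calcium |
| Analytes collected | Protocol 10.5 | Calcium, total protein; no albumin, no ionized calcium |
| Analytes grouped for summary | SAP 11.8.3 | Calcium, total protein; no albumin, no ionized calcium |
| Grading rule | SAP 11.8.3.1 | Numeric SI value of the assessed parameter |
| Correction formula or fallback | SAP | None found |

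**2. Is calcium really among the graded parameters?** SAP 11.8.3.1 counts 5 hematology and 10 chemistry parameters. The chemistry list is alkaline phosphatase, ALT, AST, bilirubin, calcium, creatinine, glucose, potassium, sodium and triglycerides. That makes 10 only with calcium included, so calcium is graded, and 5 + 10 = 15.

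**3. Are the cut-offs themselves usable?** Dividing the mg/dL limits by 4.008 gives 8.0 → 1.996, 7.0 → 1.747, 6.0 → 1.497, 11.5 → 2.869, 12.5 → 3.119 and 13.5 → 3.368 mmol/L. The printed values are 2.0, 1.75, 1.5, 2.9, 3.1 and 3.4. The unit pairs agree after rounding, so the gap is the missing input and not the conversion.

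**4. Illustration of the possible shift.** Assumptions that are not in the documents: the correction is for albumin, corrected = reported + 0.02 × (40 − albumin in g/L) mmol/L; LLN 2.15 and ULN 2.55 mmol/L.

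| Albumin (g/L) | Shift (mmol/L) | Reported → corrected | Grade as reported → corrected |
|---|---|---|---|
| 30 | 0.02 × 10 = +0.20 | 2.05 → 2.25 | Hypocalcemia 1 → 0 |
| 30 | +0.20 | 2.50 → 2.70 | Hypercalcemia 0 → 1 |
| 35 | 0.02 × 5 = +0.10 | 1.95 → 2.05 | Hypocalcemia 2 → 1 |
| 40 | 0 | any | No change |
| 45 | 0.02 × (−5) = −0.10 | 2.20 → 2.10 | Hypocalcemia 0 → 1 |
| 45 | −0.10 | 2.60 → 2.50 | Hypercalcemia 1 → 0 |

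For scale, the Grade 2 hypocalcemia band is 2.0 − 1.75 = 0.25 mmol/L wide. The Grade 1 band, with the assumed LLN, is 2.15 − 2.0 = 0.15 mmol/L wide. A shift of 0.10 to 0.20 mmol/L can therefore cross a limit, but only for values that already lie within that distance of it.

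The documents give no distribution of albumin or calcium, so no share of affected subjects is estimated.

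**The case against.** The case on the other side is substantial and narrows the point.

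- **Not listed is not the same as not measured.** A reader might infer that albumin and ionized calcium were never assayed. The documents do not support that. Protocol 10.5 introduces the panel with the word including, and the laboratory manuals are not available. The groups in SAP 11.8.3 are not a full inventory: glucose is graded in 11.8.3.1 and conjugated bilirubin is in the protocol panel, yet neither appears in those groups. The SAP team did compare the laboratory transfers with grading needs for lymphocytes and neutrophils, so silence on calcium could mean that nothing was missing. This stands.
- **Misgrading is possible, not certain.** A reader might also infer that subjects with low albumin would be falsely graded for hypocalcemia and their hypercalcemia missed. A grade changes only when albumin is away from the reference value and calcium is near a limit, and high albumin reverses the direction. Nothing suggests that markedly low albumin is common here: Protocol 8.4.2 excludes clinically significant chemistry results at screening and worsening end-stage renal disease. This stands too.
- **Clinical signals have other routes.** Under Protocol 11.5.1, laboratory changes judged clinically significant become adverse events, and unexplained abnormal results are repeated. SAP 11.8.3 also summarizes values and changes by visit and arm.
- **The numeric-value rule already settles it.** This fails. The examples after that rule concern clinical signs and symptoms. It does not say that uncorrected calcium may stand in for corrected calcium, nor that the output will be labelled as such.

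**Conclusion.** The point holds as a gap in specification and labelling. With the analytes listed, the calcium grades cannot be derived as Appendix 2 defines them, and the SAP does not say what to do instead. Following 11.8.3.1 literally would report uncorrected calcium under CTCAE names.

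The size is small. Under the assumed albumin correction the discrepancy is about −0.10 to +0.20 mmol/L for albumin from 45 down to 30 g/L, and zero at 40 g/L. The formula, the albumin values and the reference limits are all assumptions. The exposure is confined to the calcium rows of a descriptive maximum-grade table and the Grade 3 or higher listing, with no test or margin attached. Nothing in the documents suggests that albumin would differ between randomized arms, so any error should fall on both about equally. The antibody equivalence and HbA1c conclusions are unaffected.

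Even if albumin was transferred, the gap remains, because no correction rule is written down.

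**What to change.** First, check whether the central laboratory transfer contains albumin.

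- **If it does:** state the correction formula in SAP 11.8.3.1, as was done for lymphocytes and neutrophils, and grade corrected calcium.
- **If it does not:** keep the rows but label them 'calcium, uncorrected' and do not present them as CTCAE hypo- or hypercalcemia. Alternatively, remove calcium from the graded parameters in 11.8.3.1 and Appendix 2, so that the chemistry count goes from 10 to 9 and the total from 15 to 14. Dropping the grades loses no calcium data, because 11.8.3 already plans shift tables by central-laboratory reference range covering all laboratory assessments.

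The cost is a few lines of SAP text and the matching calcium entries in the table and listing shells. No new tests or samples are needed. SAP 10.3 describes database lock as still to come, so the change can be made before lock.

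While the calcium rows are open, correct one separate defect: the Grade 2 hypercalcemia cell repeats the Grade 1 range, which leaves values above 2.9 and up to 3.1 mmol/L without a grade. That error exists whatever is decided about correction.
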